6.3.9 Dose Modification and Monitoring for Mucositis

6.3.10 Dose Modifications, Monitoring, and Stopping Rules for Visual Disturbance

Episodes of visual changes have been observed in subjects receiving trametinib, and ocular adverse events are known to be related to trametinib. An ophthalmologist should be consulted if changes in vision develop. However, if the visual changes are clearly unrelated to study treatment (e.g. allergic conjunctivitis), monitor closely but ophthalmic examination can be deferred. Special attention should be given to retinal findings (e.g. retinal pigment epithelial detachment (RPED), retinal vein abnormalities (e.g. branch or central retinal vein occlusions (RVO)), or optic nerve swelling.

Guidelines regarding management and dose reduction for visual changes and/or ophthalmic examination findings considered to be related to study treatment are provided in the tables below:

Table 6.3.10 A:	Management and Dose Modification Guidelines for Visual
	Changes and/or Ophthalmic Examination Findings
Table 6.3.10 B:	NCI-CTCAE v 4.0: "Eye Disorders - Other, specify"
Table 6.3.10 C:	Recommended dose modifications for trametinib for retinal
	pigment epithelial detachments (RPED)
Table 6.3.10 D:	NCI-CTCAE v 4.0: "Retinopathy"

Ophthalmologic Exam

At certain time points in the trial and if visual changes develop, an eye exam is indicated. (Refer to Table 6.3.10 A for visual changes stopping criteria). The exam will include best corrected visual acuity, visual field examination, tonometry, slit lamp biomicroscopic examination, and indirect fundoscopy, with special attention to retinal abnormalities. Optical coherence tomography is recommended at scheduled visits and if retinal abnormalities are suspected. Other types of ancillary testing including visual field examination, fundus photography, and fluorescein angiography may also be indicated as determined by clinical exam.

Table 6.3.10 A:	Management and Dose N	Modification Guidelines for Visual Changes
	and/or Ophthalmic Examination Findings	
CTCAE Grade ^a	Adverse Event Management	Action and Dose Modification
Grade 1 ^b	 Consult ophthalmologist within 7 days of onset 	 If dilated fundus examination cannot be performed within 7 days of onset, interrupt trametinib until RPED, and RVO can be excluded by retina specialist/ophthalmologist. If RPED and RVO excluded, continue (or restart) trametinib at same dose level If RPED suspected or confirmed: see RPED dose modification table below; report as SAE. If RVO diagnosed: Permanently discontinue trametinib and report as SAE.
	 Consult ophthalmologist 	 If RPED and RVO excluded and ophthalmic
Grade 2 and Grade 3	immediately • Interrupt trametinib	 findings are consistent with an alternative suspected trametinib-related ocular adverse event (e.g., optic neuropathy), and signs and symptoms resolve to baseline, resume trametinib at a lower dose (reduced by 0.5 mg) or discontinue trametinib in patients taking 1 mg daily. If RPED and RVO excluded and ophthalmic findings are NOT consistent with an alternative suspected trametinib-related ocular adverse event (e.g., optic neuropathy), restart trametinib at same dose level If RPED diagnosed, see RPED dose modification table below; report as SAE. If RVO diagnosed: Permanently discontinue trametinib, and report as SAE
	Consult onbthalmologist	If BVO or BPED then permanently discontinue
Grade 4	immediately	 trametinib and report as SAE If RPED and RVO excluded and ophthalmic findings are consistent with an alternative suspected trametinib-related ocular adverse event (e.g. optic neuropathy), then permanently discontinue trametinib and report as SAE If RPED and RVO excluded, and ophthalmic findings are NOT consistent with an alternative suspected trametinib-related ocular adverse event, interrupt treatment with trametinib and report as n SAE. If signs and symptoms resolve to baseline, may consider restarting trametinib at same or reduced dose

a. Refers to CTCAE Version 4.0 'Eye disorders – Other, specify,' as detailed in Table 6.3.10 B, below

b. If visual changes are clearly unrelated to study treatment (e.g., allergic conjunctivitis), monitor closely but ophthalmic examination is not required.

Table 6.3.10 B: NCI-CTCAE v 4.0: 'Eye Disorders - Other, specify'	
Grade	Description
1	Asymptomatic or mild symptoms; clinical or diagnostic observations only; intervention not indicated
2	Moderate; minimal, local or non-invasive intervention indicated; limiting age- appropriate instrumental activities of daily living (ADL)
3	Severe or medically significant but not immediately sight-threatening; hospitalization or prolongation of existing hospitalization indicated; disabling; limiting self care ADL
4	Sight-threatening consequences; urgent intervention indicated; blindness (20/200 or worse) in the affected eye

Table 6.3.10 C: Recommended dose modifications for trametinib for retinal pigment epithelial detachments (RPED)^a

Grade 1 RPED (Asymptomatic; clinical or diagnostic observations only)	 Continue treatment with retinal evaluation monthly until resolution. If RPED worsens follow instructions below and withhold trametinib for up to 3 weeks 	
Grade 2-3 RPED (Symptomatic with Mild to moderate decrease in visual acuity; limiting instrumental ADL	Withhold trametinib for up to 3 weeks	
Grade 2-3 RPED that improves to Grade 0-1 within 3 weeks	 If improved within 3 weeks, resume trametinib at a lower dose (reduced by 0.5 mg) or discontinue trametinib in patients taking trametinib 1 mg daily 	
Grade 2-3 RPED that does not improve to at least Grade 1 within 3 weeks	Permanently discontinue trametinib	

a. Refers to CTCAE Version 4.0 'Retinopathy,' as detailed in Table 6.3.10 D, below

Table 6.3.10 D: NCI-CTCAE v 4.0: 'Retinopathy'	
Grade	Description
1	Asymptomatic; clinical or diagnostic observations only
2	Symptomatic with moderate decrease in visual acuity (20/40 or better); limiting instrumental ADL
3	Symptomatic with marked decrease in visual acuity (worse than 20/40); disabling; limiting self care ADL
4	Blindness (20/200 or worse) in the affected eye

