6.4 Dose Adjustment/Stopping Safety Criteria for Other Clinically Significant Toxicities

Dose modification guidelines are outlined in the table below for clinically significant toxicities, including hematologic toxicities, that are deemed related to study medication(s) but are not addressed above. If a given toxicity is considered by the

investigator to be related to a single investigational drug and not both, then dose modification may occur only with the drug associated with a specific toxicity or event of clinical concern.

Dose Modification Guidelines for GSK1120212 (trametinib) and/or GSK2141795	
Toxicity Grade ^a	Dose Modification of GSK1120212 (trametinib) and/or GSK2141795
Grade 1	Continue at current dose level. Consider supportive care recommendations.
Grade 2	Consider withholding dose until toxicity resolves to Grade 1 or baseline. Upon resolution, then restart at current dose level. Consider supportive care recommendations.
Grade 3	Withhold dose until toxicity resolves to Grade 1 or baseline. Upon resolution, then consider dose reducing by next lower dose level. Consider supportive care recommendations.
Grade 4	Permanently discontinue study medications.

a. Considered related to study drug.

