6.4.2 Additional Toxicities

Other toxicities are possible on this trial. Participants developing drug-associated grade 3 or 4 non-hematological toxicities or grade 4 hematological toxicities that do not resolve or improve to grade 1 within 21 days will be removed from protocol. Participants whose toxicity has resolved to baseline or Grade 1 and whose therapy has been discontinued for fewer than 21 days may resume therapy with 1 level of dose reduction.

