APPENDIX F: CTCAE v 4.0 Grading of Visual Changes

Visual Changes - Grading Based on NCI-CTCAE v 4.0

Grade	Description
1	Asymptomatic or symptomatic but not limiting ADL; clinical or diagnostic observations only; intervention not indicated
2	Symptomatic with moderate decrease in visual acuity (20/40 or better); limiting instrumental ADL; local or noninvasive intervention indicated (e.g., topical or oral agents)
3	Symptomatic with marked decrease in visual acuity or marked visual field defect (worse than 20/40 but better than 20/200 in the affected eye); Severe pain or medically significant but not immediately sight-threatening; operative intervention indicated; disabling; limiting self care ADL
4	Sight-threatening consequences; urgent intervention indicated; blindness (20/200 or worse) in the affected eye

Ophthalmologic Exam

Subjects are required to have a standard ophthalmic exam performed by an ophthalmologist at baseline and as clinically warranted per protocol's guidance (Refer to Section 6.3.9 for visual changes stopping criteria). The exam will include indirect fundoscopic examination, visual acuity (corrected), visual field examination, tonometry, and direct fundoscopy, with special attention to retinal abnormality that are predisposing factors for RVO or CSR.

For participants with clinical suspicion of RVO or CSR, fluorescein angiography and/or optical coherence tomography are highly recommended.

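### Table 6.3.10 A, as read from the PDF, holds trametinib at onset of a Grade 2-3 visual event but not of a Grade 4 one: a low-priority drafting gap to check and close

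*Combined protocol and SAP*

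**What the plan says.** The introduction to section 6.3.10 says that guidelines for visual changes and/or "ophthalmic examination findings considered to be related to study treatment are provided in the tables below". The tables therefore cover events already attributed to treatment. Events that are clearly unrelated need only close monitoring.

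Table 6.3.10 A has a management column and an action column.

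- **Grade 1:** consult within 7 days of onset. Trametinib is interrupted if a dilated fundus examination cannot be done in that time.
- **Grades 2 and 3:** the management cell orders an immediate consult and, as a separate bullet with no condition attached, "interrupt trametinib". The action column then says what to do once the findings are known.
- **Grade 4:** the management cell orders an immediate consult and, in the text as read, nothing else. The action column has three branches. Retinal vein occlusion (RVO) or retinal pigment epithelial detachment (RPED) means permanent discontinuation. Another suspected trametinib-related eye event also means permanent discontinuation. If neither applies, the site is to "interrupt treatment with trametinib and report as n SAE", with restart possible on recovery.

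Table 6.3.10 B defines Grade 4 as "Sight-threatening consequences; urgent intervention indicated; blindness (20/200 or worse) in the affected eye".

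**The concern.** Daily dosing is the default under section 5.2.1, so an event that triggers no written hold leaves the participant on drug unless the investigator decides otherwise. Followed literally, the table takes a participant with a Grade 2 visual event off trametinib at once. A participant with a sight-threatening event stays on it until the ophthalmologist reports. A stopping rule should not leave the most severe grade to inference when the grade below it is explicit. What is at stake is a short period of avoidable exposure in a few participants. No efficacy result depends on it.

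**Working it through.** The plan states no figure on this point, so there is none to reproduce. The check is a side-by-side reading, followed by a small calculation of exposure.

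**Step 1. Table 6.3.10 A, row by row.**

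| Grade | Trametinib before findings are known | Trametinib after findings |
|---|---|---|
| 1 | Held only if no fundus examination within 7 days | Same dose if RPED and RVO are excluded; RPED goes to Table C; RVO stops it permanently |
| 2-3 | Held, no condition | Resume lower, restart at the same dose, or Table C; RVO stops it permanently |
| 4 | No instruction | Permanent stop in two branches; interruption with possible restart in the third |

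After the examination the Grade 4 row is the stricter one: RPED ends treatment, whereas Grade 2-3 RPED may resume. The gap lies only in the middle column.

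**Step 2. Does another rule order the hold?**

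- Section 5.1.2 sets toxicity limits for Day 1 of later cycles only.
- Table 6.3.10 C tells sites to "withhold trametinib for up to 3 weeks" for Grade 2-3 RPED. It has no Grade 4 row and presupposes a diagnosis.
- The general table in section 6.4 stops drug at Grade 4, but only for toxicities "that are deemed related to study medication(s) but are not addressed above". Visual events are addressed above.
- Section 6.4.2 acts at 21 days. It says that recovered participants "whose therapy has been discontinued for fewer than 21 days may resume therapy", which presupposes an interruption without ordering one.
- Appendix F gives grades without drug actions. Its pointer, "Refer to Section 6.3.9 for visual changes stopping criteria", leads to the mucositis section.
- Sections 5.4, 6 and 6.1.3 leave room for a hold through their language on unacceptable events, severity-based modification and active ocular management. None orders one.

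No rule orders a hold at onset of Grade 4.

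**Step 3. Comparison with other toxicities.** Seven other tables in sections 6.3 and 6.4 attach an action to a CTCAE Grade 4 event. Six of them (rash, diarrhea, LVEF, pneumonitis, mucositis and the general table) hold or stop drug once the grade is met. The seventh, QTc, does so after averaging triplicate ECGs. Hypertension (section 6.3.6) falls outside that count and is a counter-example. In its Scenario B (asymptomatic, systolic at least 160 or diastolic at least 100 mm Hg), interrupting trametinib is left to clinical indication. Discretionary holds therefore do exist in this protocol.

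**Step 4. Size.** Inputs: starting dose 1.5 mg once daily (section 5.2.1) and mean effective half-life of about 5 days (section 2.2.1, Effects in Humans). The documents give no time to examination, so 1 to 2 days is an assumption.

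- Extra drug = 1.5 mg × doses. Seen within 1 day: 0 to 1 dose, at most 1.5 × 1 = 1.5 mg. Seen within 2 days: at most 1.5 × 2 = 3.0 mg.
- Level remaining after d days without a dose, from steady state with first-order decline = 2^(−d/5). For d = 1, 2^(−0.2) = 0.871, or 12.9% lower. For d = 2, 2^(−0.4) = 0.758, or 24.2% lower.

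A prompt hold would thus lower the level by roughly an eighth to a quarter by the time of the examination.

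**The case against.** The strongest objection is that the evidence is an absence in a row that was visibly misread. In the first Grade 4 line, letters are wrong in the word for the specialist and in both retinal abbreviations, and the bullet marks are gone, while the rows above keep theirs. The missing item would be one short bullet in that same cell. This stands as a limit. Loss is possible, though the rest of the row reads as complete, so the original table has to be checked before anything is changed.

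A reader might infer from the third branch, where the order to interrupt comes only after RPED and RVO are excluded, that dosing was meant to continue until then. The documents do not support that. Section 6.3.10 repeats holds that are already in force: the Grade 2-3 row interrupts trametinib and then sends RPED to Table C, which withholds it again. In the Grade 4 row the word may simply contrast with permanent discontinuation in the other two branches. The point rests on the missing instruction alone.

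It is also fair to say that the three branches cover every outcome and that each interrupts or stops trametinib. An investigator can see at onset where the row leads, and many would hold the drug on their own judgement. A participant who worsens through Grade 2 or 3 should already be off trametinib under that row. Because Grade 4 is partly defined by measured acuity, some assessment may come before the grade is assigned. All of this stands. It makes the gap small but does not supply the missing instruction.

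**Conclusion.** The point holds as a low-priority drafting omission, provided the original table confirms it. The Grade 4 row orders no hold of trametinib while findings are pending, the Grade 2-3 row does, and no other section fills the gap. Nothing suggests that anyone chose this, and nothing in the documents orders dosing to continue.

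It matters only for participants whose visual event is first recognised at Grade 4, and only until a consult that is already ordered as immediate. On the assumed delay of 1 to 2 days it amounts to 0 to 2 doses. The documents give no rate for such events among the 35 planned participants and show no effect of one or two doses on the eye outcome. The response endpoint, power and analysis are unaffected.

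A reader might also take the eye table to be the protocol's only departure from a mandatory hold for severe toxicity. The discretionary hold for hypertension in section 6.3.6 shows that it is not.

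**What to change.** First confirm in the original PDF that the Grade 4 management cell lacks the instruction. If it is there, no change is needed.

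If it is absent:

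1. Add the Grade 2-3 instruction, "interrupt trametinib", to the Grade 4 management cell.
2. Keep the three branches as the rules for after the examination.
3. Reword the third branch to: *keep trametinib interrupted and report as an SAE*.

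Bundle this with the next amendment; it does not need one of its own. The cost is IRB review of one line at each site (section 13.1) and the 0 to 2 doses (0 to 3.0 mg) forgone while the examination is pending. No visits, procedures or participants are added. Because no Grade 4 branch allows uninterrupted dosing, no other treatment is given up.

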6.4 Dose Adjustment/Stopping Safety Criteria for Other Clinically Significant Toxicities

Dose modification guidelines are outlined in the table below for clinically significant toxicities, including hematologic toxicities, that are deemed related to study medication(s) but are not addressed above. If a given toxicity is considered by the

investigator to be related to a single investigational drug and not both, then dose modification may occur only with the drug associated with a specific toxicity or event of clinical concern.

Dose Modification Guidelines for GSK1120212 (trametinib) and/or GSK2141795	
Toxicity Grade ^a	Dose Modification of GSK1120212 (trametinib) and/or GSK2141795
Grade 1	Continue at current dose level. Consider supportive care recommendations.
Grade 2	Consider withholding dose until toxicity resolves to Grade 1 or baseline. Upon resolution, then restart at current dose level. Consider supportive care recommendations.
Grade 3	Withhold dose until toxicity resolves to Grade 1 or baseline. Upon resolution, then consider dose reducing by next lower dose level. Consider supportive care recommendations.
Grade 4	Permanently discontinue study medications.

a. Considered related to study drug.

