Uncomplicated Diarrhea, ¹ Grade 3 or 4 and Any Complicated Diarrhea ²	 Clinical evaluation mandatory. Loperamide³: Initially 4 mg, followed by 2 mg every 4 hours or after every unformed stool; maximum 16 mg/day. Continue until diarrhea-free for 12 hours. Oral antibiotics and second-line therapies if clinically indicated Hydration: Intravenous fluids if clinically indicated. Antibiotics (oral or intravenous) if clinically indicated. Intervention should be continued until the subject is diarrhea-free for ≥24 hours. Intervention may require hospitalization for subjects at risk of 	 Interrupt BOTH agents until diarrhea resolves to ≤ grade 1. Restart with trametinib or GSK2141795 reduced by one dose level (for the combination, reduce both agents by one level).⁴ If more than one dose reduction of study treatment is clinically indicated, permanently discontinue treatment. If treatment delay is >21 days, discontinue treatment. (resumption of trametinib or GSK2141795 alone may be considered based on toxicity-benefit consideration and after consultation with PI)
1 Uncomplicat	life-threatening complications.	matems such as gramping, house a homiting >
 Uncomplicated diarrnea defined by the absence of symptoms such as cramping, hausea/vomiting, ≥ grade 2, decreased performance status, pyrexia, sepsis, neutropenia ≥ grade 3, frank bleeding, and/or dehydration requiring intravenous fluid substitution. Complicated diarrhea defined by the presence of symptoms such as cramping, nausea/vomiting, ≥ grade 2, decreased performance status, pyrexia, sepsis, neutropenia ≥ grade 3, frank bleeding, and/or grade 2, decreased performance status, pyrexia, sepsis, neutropenia ≥ grade 3, frank bleeding, and/or grade 2, decreased performance status, pyrexia, sepsis, neutropenia ≥ grade 3, frank bleeding, and/or 		
dehydration 3. Loperamide	dehydration requiring intravenous fluid substitution.3. Loperamide should be made available prior to start of study treatment so loperamide administration	
4. Escalation of with the PI a subsequent	 Escalation of trametinib and/or GSK2141795 to previous dose level(s) is allowed after consultation with the PI and in the absence of another episode of complicated or severe diarrhea in the 4 weeks subsequent to dose reduction. 	

6.3.3 GSK2141795 Dose Modification and Management Guidelines for Hypo- or Hyperglycemia

Hyperglycemia has been associated with treatment with GSK2141795.

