Grade 1 or 2	Encourage oral hygiene. Offer topical supportive anesthetics. Encourage adequate hydration.
Grade 3 or 4	As above, plus systemic opiate administration as needed. Consider IV hydration and hospital admission as appropriate. Temporarily discontinue study drug(s).

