6.4.1 Management of Fever and Neutropenia

Participants who develop fever and neutropenia will be managed via standard medical practice and American Society of Clinical Oncology and NCCN guidelines. Participants will need to recover from fever and active infectious issues prior to resuming therapy. Use of growth factors may be considered after discussion with the primary investigator.

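### For a drug-related Grade 4 toxicity without its own rule in 6.3, the 6.4 table says stop for good while 6.4.2 permits resumption one level down; secondarily, the QTc hold starts on QTcF but ends on QTcB

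*Combined protocol and SAP*

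**What the plan says.** Section 6.4 contains a catch-all guideline table for clinically significant toxicities, "including hematologic toxicities, that are deemed related to study medication(s) but are not addressed above". Its Grade 3 row is a hold followed by a possible one-level reduction. Its Grade 4 row reads "Permanently discontinue study medications" and has no exception or rechallenge clause. The paragraph above the table adds that, when the investigator attributes an event to one agent, "dose modification may occur only with the drug associated with a specific toxicity or event of clinical concern".

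Section 6.4.2 sits under the same heading. It covers drug-associated non-hematologic events of Grade 3 or 4 and hematologic events of Grade 4. For the hematologic group it states that those who develop "grade 4 hematological toxicities that do not resolve or improve to grade 1 within 21 days will be removed from protocol"; the same 21-day test applies to the non-hematologic group. It continues: "Participants whose toxicity has resolved to baseline or Grade 1 and whose therapy has been discontinued for fewer than 21 days may resume therapy", at one dose level lower. That sentence names no grade.

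The dose table in Section 6 lists one reduced level, -1: trametinib 1.0 mg (from 1.5 mg) and GSK2141795 25 mg (from 50 mg).

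On QTc, Section 6.3.7 starts a hold at QTcF of 501 msec or more, at QTcF above 530 msec with bundle branch block, or at uncorrected QT above 600 msec. The hold ends when QTcB has returned to Grade 1 or to baseline. The text refers to Appendix I for the correction, but Appendix I is Data Collection Forms. The formula is in Appendix K, which gives Bazett only.

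**The concern.** Both provisions cover the same residual class: Grade 4, related to study drug, no rule of its own in 6.3. One ends treatment. The other allows it to continue at a lower dose after recovery. In a multicenter trial, two sites could handle the same event differently and each could cite the protocol. The site that resumes would re-expose a patient whom the 6.4 table says should stop.

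The class is plausible for these agents. Section 6.1.5 lists thrombocytopenia among the commonly reported trametinib events, although without grades.

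The QTc point is smaller but similar in kind: the hold is triggered on one scale and released on another.

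**Working it through.** The main point is a comparison of texts; the plan states no figure to reproduce.

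**1. Do the two provisions overlap?**

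| | Section 6.4 table | Section 6.4.2 |
|---|---|---|
| Events | Related, not addressed earlier, hematologic included | Drug-associated; Grade 3 or 4 non-hematologic, Grade 4 hematologic |
| Grade 3 | Hold, then consider one level down | May resume one level down if off for under 21 days |
| Grade 4, resolved in under 21 days | Permanent stop | May resume one level down |
| Grade 4, unresolved at 21 days | Permanent stop | Removed from protocol |

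The Grade 3 entries are compatible. So are the entries for unresolved Grade 4 events. The conflict is in the third row. Grade 4 is in the 6.4.2 population, the resumption sentence does not exclude it, and no text ranks the sections.

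**2. Does the single-drug clause remove the conflict?** No. It narrows which drug is modified. It does not let the responsible drug restart after a Grade 4 event.

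**3. Do neighbouring rules show the intent?** They point both ways.
- Diarrhea of Grade 3 or 4 (6.3.2): "Restart with trametinib or GSK2141795 reduced by one dose level".
- Mucositis of Grade 3 or 4 (6.3.9): a temporary stop.
- QTc prolongation of Grade 3 or 4 (6.3.7): restart at the current dose; stop permanently on recurrence.
- Symptomatic Grade 4 LVEF decrease (6.3.4): both drugs stopped permanently.
- Fever with neutropenia (6.4.1): "Participants will need to recover from fever and active infectious issues prior to resuming therapy", with no grade or dose level given.

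**4. Size of the difference.** For an attributed drug at its starting dose, one reading gives zero. The other gives 1.0/1.5 = 67% of the starting dose for trametinib, or 25/50 = 50% for GSK2141795. No level below -1 is listed, so a participant already there has no lower dose to resume at.

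**5. QTc scales.** Appendix K gives QTcB = QT/RR^(1/2), with RR = 60/HR. The documents do not print Fridericia; I assume the standard form, QTcF = QT/RR^(1/3). Then QTcB/QTcF = RR^(-1/6). For an ECG exactly at the QTcF trigger of 501 msec:

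| Heart rate (bpm) | RR^(-1/6) | QTcB (msec) |
|---|---|---|
| 45 | 0.9532 | 477.5 |
| 50 | 0.9701 | 486.0 |
| 60 | 1.0000 | 501.0 |
| 75 | 1.0379 | 520.0 |
| 90 | 1.0699 | 536.0 |

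The scales agree only at 60 bpm. Bazett reads lower than Fridericia below that rate and higher above it, so release on QTcB is looser at slow heart rates and stricter at fast ones. The table describes the trigger. It does not measure a gap at release, because release is at Grade 1 or baseline and the documents give no millisecond range for Grade 1.

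**The case against.** The best defence is that the sections can be read together: 6.4 sets the action by grade, and 6.4.2 sets a time limit on interruptions. The 6.4 table is headed as guidelines, Section 6 calls its rules recommendations, and resumption under 6.4.2 is optional. All of that is true, and it means 6.4 should not be described as an absolute requirement. It does not reconcile the texts, because the guideline label favours neither section and the Grade 4 row remains unconditional.

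A reader might infer that the hematologic part of 6.4.2, which names only Grade 4, would be empty if 6.4 governed, and hence that 6.4.2 must intend Grade 4 resumption. The documents do not support that. Under the single-drug clause, a participant could stop only the attributed drug and continue the other. The 21-day rule would then decide whether she leaves the protocol altogether, so that part keeps a function.

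The affected class is also narrow. Liver chemistry, hypertension, rash, glucose and visual events all have their own rules in 6.3. From Cycle 2, Section 5.1 requires ANC of at least 1,000/mcL and platelets of at least 75,000/mcL on Day 1, but that check does not say whether someone with a Grade 4 event may return.

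Reporting helps detection. Under 11.4.1, Grade 4 events that are unexpected or not listed as exempt go to the Overall Principal Investigator within 1 business day. Under 12.2, the monitoring committee reviews toxicity quarterly. Neither supplies the missing rule.

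On QTc, restart needs agreement between the investigator and the medical monitor, which limits the risk. The footnote that says so refers to QTc without naming a correction.

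**Conclusion.** The inconsistency stands and should be fixed. For residual drug-related Grade 4 events that settle with therapy off for fewer than 21 days, the protocol gives two answers: no drug, or level -1 for the attributed drug or drugs. This follows from the text and needs no outside assumption.

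Its limits are these. Stopping is consistent with both sections, so no site is forced into a breach. The documents give no Grade 4 rate for this class, so no frequency can be stated. A reader might infer that inconsistent dosing undermines the response-rate test in 14.2; nothing in the documents shows such an effect and none is claimed.

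The QTc mismatch is real but minor. Its direction by heart rate depends on the standard Fridericia formula. A reader might take the 501 msec table as the size of an early or late release; it is not, for the reason given with the table.

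**What to change.** State one Grade 4 action for the residual class.

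- **Default:** limit the 6.4.2 resumption sentence to Grade 3 events, for the attributed drug. Keep the 21-day removal rule for unresolved Grade 3 or 4 non-hematologic and Grade 4 hematologic events.
- **Alternative, if the clinical team intends it:** write an explicit exception into the 6.4 Grade 4 row, for example that hematologic events resolved within 21 days resume one level down.

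In either case, say whether the Grade 4 row means both drugs or only the attributed one, and that a participant already at level -1 stops that drug.

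In 6.3.7, make QTcF the release measure; it is already the trigger and the eligibility measure (3.2.20). Add the Fridericia formula to Appendix K and redirect the Appendix I reference there.

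The cost is a protocol wording amendment, with no new procedures or patients.
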